- 5) If an SAE occurred, follow the instructions in [Section 10](#) for reporting it. Remind to notify the site in case of an SAE.
- 6) Complete the relevant CRFs for this visit.
- 7) Remind the parent / guardian / legally acceptable representative of the following visit.

Visit 03: Day 56+7 Post-Vaccination 1 Visit Procedures for Cohort 1 and 3

- 1) Review medical history, including past and ongoing medication since the last visit. Check for contraindications.
- 2) Perform a focused clinical examination including temperature, pulse, and respirations, EENT, respiratory, cardiac and lymphatic system.
- 3) Obtain a blood sample for serum antibodies to RSV (see [Section 7.1](#) for detailed instructions regarding the handling of blood samples).
- 4) Collect and review SAEs in the completed DC1 and DC2 / eDC with the participant's parent / guardian / legally authorized representative. Provide MA.
- 5) If an SAE had occurred, follow the instructions in [Section 10](#) for reporting it. Remind to notify the site in case of an SAE.
- 6) Complete the relevant CRFs for this visit.
- 7) Remind the parent / guardian / legally authorized representative of the following visit.

Visit 03: Day 56+7 Post-Vaccination 1 Visit Procedures for Cohorts 2 and 4

- 1) Obtain verbal medical history about the participant, including past and ongoing medication and immunizations.
- 2) Check for contraindications for receipt of second vaccination.
- 3) Prior to vaccination, conduct a focused clinical examination including temperature, pulse, and respirations, EENT, respiratory, cardiac and lymphatic system.
- 4) Perform COVID-19 POC diagnostic test.
- 5) Collect reportable concomitant medications / vaccinations.

- 6) Contact the IRT for dose number.
- 7) Obtain a blood sample for serum antibodies to RSV (see [Section 7.1](#) for detailed instructions regarding the handling of blood samples).
- 8) Administer the appropriate study product, follow the instructions provided for the intranasal administration of study vaccine using the [REDACTED] in the Study Operating Guideline.
- 9) Keep the participant under observation for 30 minutes and record any adverse reaction in the source document.
- 10) Collect and review solicited reactions and unsolicited AEs, including AESIs, MAAEs and SAEs in the completed DC1 and DC2 / eDC with the participant's parent / guardian / legally authorized representative.

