5.2.7.2 Definitive Contraindications

Should a participant experience one of the conditions listed below, the Investigator will discontinue vaccination:

- 1) An anaphylactic or any other significant allergic reaction to the previous dose of vaccine.
- 2) Any AE greater than Grade 2, LRI of any grade or SAE assessed by the investigator as related to the previous dose of vaccine.
- 3) Diagnosis of COVID-19

Participants with a definitive contraindication will continue to be followed up for the study-defined safety and immunogenicity assessments, as applicable.

In the event of a local or national immunization program with a pandemic vaccine e.g. influenza, participants who receive pandemic vaccine at any time during the study will not be withdrawn from the study.

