Medical and scientific judgment should be exercised in deciding whether expedited reporting is appropriate in other situations, such as IMEs that may not be immediately life-threatening or result in death or hospitalization but may jeopardize the health of the participant or may require intervention to prevent one of the other outcomes listed in the definition above. These IMEs should also usually be considered serious. Examples of such events include allergic bronchospasm requiring intensive treatment in an emergency room or at home, blood dyscrasias or convulsions that do not result in inpatient hospitalization, or the development of drug dependency or drug abuse, new-onset diabetes, or auto-immune disease.

^a The term “life-threatening” refers to an event in which the participant was at risk of death at the time of the event; it does not refer to an event which hypothetically might have caused death if it were more severe.

^b All medical events leading to hospitalizations will be recorded and reported as SAEs, with the exception of: hospitalization planned before inclusion into the study or outpatient treatment with no hospitalization.

^c “Persistent or significant disability or incapacity” means that there is a substantial disruption of a person’s ability to carry out normal life functions.

Adverse Reaction:

All noxious and unintended responses to a medicinal product related to any dose should be considered adverse reactions (AR).

(The phrase “responses to a medicinal product” means that a causal relationship between a medicinal product and an AE is at least a reasonable possibility)

The following additional definitions are used by Sanofi Pasteur:

Immediate Event/Reaction:

Immediate events are recorded to capture medically relevant unsolicited systemic AEs (including those related to the product administered) that occur within the first 30 minutes after vaccination.

Solicited Reaction:

A solicited reaction is an “expected” adverse reaction (sign or symptom) observed and reported under the conditions (nature and onset) pre-listed in the protocol and CRB (e.g., fever and runny nose occurring between D0 and D28 post-vaccination).

By definition, solicited reactions are to be considered as being related to the product administered. For vaccines administered nasally, solicited reactions can either be solicited administration site reactions or solicited systemic reactions.

Unsolicited AE / AR:

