Intensity scale*	
Grade 1 (mild): No medical intervention required; may include use of over-the-counter medications managed by the caregiver for treatment of symptoms
 
Grade 2 (moderate): Outpatient medical intervention by a health care provider required; may include use of over-the-counter and/or prescription medications
 
Grade 3 (severe): Prolonged medical intervention and/or hospitalization required
 
Grade 4 (life-threatening): Illness requiring hospitalization with intensive care
 
Grade 5 (death): Event resulting in fatal outcome to the participant
	
Grade 1 (mild): No medical intervention required; may include use of over-the-counter medications managed by the caregiver for treatment of symptoms
 
Grade 2 (moderate): Outpatient medical intervention by a health care provider required; may include use of over-the-counter and/or prescription medications
 
Grade 3 (severe): Prolonged medical intervention and/or hospitalization required
 
Grade 4 (life-threatening): Illness requiring hospitalization with intensive care
 
Grade 5 (death): Event resulting in fatal outcome to the participant

* For the measurable reactions of rhinorrhea and nasal congestion, the parent / guardian / legally authorized representative will decide whether or not medical intervention was required and if so the type of intervention, and the classification as Grade 1 - 5 will be assigned at the time of review of the diary card.

Table 9-2: Solicited systemic reactions: terminology, definitions, and intensity scales

CRB term (MedDRA lowest level term [LLT])	Fever	Vomiting	Crying abnormal	Drowsiness	Appetite lost	Irritability
Diary card term	Temperature	Vomiting	Abnormal crying	Drowsiness	Loss of appetite	Irritability
Definition	Elevation of temperature to $\geq 38.0^{\circ}\text{C}$ ($\geq 100.4^{\circ}\text{F}$)	Vomiting does not include spitting up	Inconsolable crying without a determined reason	Reduced interest in surroundings, or increased sleeping	See intensity scale	An excessive response to stimuli: increased fussiness, whining, and fretfulness despite attempts to comfort the infant and despite caregiver responses that would normally be soothing

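### For Cohorts 2 and 4, Visit 03 lists dose 2 before the final review of the completed diary, although a definitive contraindication depends on events that the diary records

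*Protocol*

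**What the plan says.** Protocol section 5.1.4.1 gives a numbered list of 14 steps for Visit 03 (Day 56+7) in Cohorts 2 and 4. The steps that matter here are:

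- Step 1: "Obtain verbal medical history about the participant, including past and ongoing medication and immunizations".
- Step 2: "Check for contraindications for receipt of second vaccination".
- Step 3: "Prior to vaccination, conduct a focused clinical examination".
- Steps 4 to 7: COVID-19 test, concomitant medications and vaccinations, IRT call for the dose number, blood sample.
- Step 8: "Administer the appropriate study product".
- Step 9: 30-minute observation.
- Step 10: "Collect and review solicited reactions and unsolicited AEs, including AESIs, MAAEs and SAEs in the completed DC1 and DC2 / eDC".

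Section 5.2.7.2 lists the conditions that end vaccination. Item 2 is "Any AE greater than Grade 2, LRI of any grade or SAE assessed by the investigator as related to the previous dose of vaccine". For solicited reactions, section 9.1.1.1 settles relatedness in advance: "By definition, solicited reactions are to be considered as being related to the product administered". For rhinorrhea and nasal congestion, the footnote to Table 9-1 says that "the classification as Grade 1 - 5 will be assigned at the time of review of the diary card".

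The diary is also looked at before Visit 03. DC1 is reviewed in person at Visit 02 (D7). Section 5.1.4.2 provides for telephone review of diary entries up to D29(+1). The Table of Study Procedures marks a DC2/eDC review at the D42(+1) call as well, but the D42 text in section 5.1.4.2 lists no such step.

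**The concern.** A check that decides whether a child may have a second dose of a live virus should draw on all the information about the first dose that is due to be reviewed at that visit. As numbered, the site takes a verbal history, checks contraindications, doses, observes, and only then collects and goes through the completed diary. If that review brings out an event that meets item 2 of section 5.2.7.2, the second dose has already been given. The stake is participant safety at dose 2. No sample size, interval or other statistical figure in the plan is affected.

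**Working it through.** **1. Is the list meant to run in time order?** Step 3 is expressly placed before vaccination. The blood sample at step 7 must precede dose 2, because section 5.1.1 defines it as the pre-dose-2 sample. The observation at step 9 can only follow step 8. The list therefore reads as chronological, and nothing in it brings the diary review forward. The Table of Study Procedures sets no order within the visit.

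**2. Which inputs to the contraindication check come before dosing?** Set against sections 5.2.7.1 and 5.2.7.2:

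| Contraindication | Visit 03 source | Before step 8? |
|---|---|---|
| Acute febrile or respiratory illness | history (1), examination (3) | yes |
| Recent vaccines or investigational products | history (1), concomitant record (5) | yes |
| COVID-19 | test (4) | yes |
| AE above Grade 2, LRI or SAE after dose 1 | history (1); completed diary (10) | history only |

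The completed diary is the only input placed after the dose. At Visit 01, by contrast, the review of past medical and immunization records (step 5) precedes administration (step 10).

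**3. What has already been reviewed?** The D7 visit covers the first week. Telephone reviews are daily, then three times weekly, then at D29(+1). Solicited reactions, unsolicited AEs, AESIs and MAAEs are entered for D0 to D28, so scheduled reviews have covered that window.

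**4. What can still be new at step 10?**

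- A paper DC2 is issued at Visit 02 and collected at Visit 03. Every scheduled review between those visits is by telephone, so this is the first scheduled in-person look at entries made after D7.
- Solicited reactions are recorded until resolution (section 9.1.1.3.2), and SAP section 4.4.1.1.1 uses a maximum intensity recorded after the solicited period. A reaction still present at D28 could worsen later.
- SAEs are recorded in the diary up to the D84 visit (section 5.1.1), so entries can be made after the last call.

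**5. Interval from the last scheduled diary review to dose 2.** Visit 03 falls on D56 to D63.

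- If the D42(+1) call counts (D42 or D43): shortest 56 − 43 = 13 days, longest 63 − 42 = 21 days.
- If only the D29(+1) call counts (D29 or D30): shortest 56 − 30 = 26 days, longest 63 − 29 = 34 days.

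**6. Who follows this list?** 40 + 180 = 220 planned children in Cohorts 2 and 4, of whom 20 + 60 + 60 = 140 are allocated to vaccine. These are the children to whom the order applies, not the number expected to have an event first found at step 10.

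**The case against.** The case for leaving the list alone is strong in several respects.

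- **Repeated review.** Besides the reviews above, staff must keep calling until contact is made (section 9.1.1.3.2), and the eDC alerts the site to respiratory symptoms (section 9.1.1.1). This stands. A reader might infer from the step order that contraindications are checked with no diary information at all; the documents do not support that.
- **Grading.** A reader might infer that nasal reactions are not graded until step 10. The Table 9-1 footnote ties grading to diary review, and the procedures table says that review takes place by telephone. Nothing defers grading to Visit 03.
- **SAEs and LRI.** Parents are to notify the site of an SAE immediately, the site has 24 hours to report it to the sponsor, and Table 5-4 sets a 2-day illness-visit timeframe. LRI findings are clinical diagnoses with the same timeframe in the Acute Phase. An event would have to escape all of this, and the verbal history at step 1, to appear first on the card.
- **List numbers are not closed gates.** Step 2 precedes the COVID-19 test and the vaccination record, both of which bear on contraindications, so the check must stay open past step 2. This stands, but those items still precede step 8; the diary review does not.
- **No outright contradiction.** Step 2 requires the check before dosing. It would be too much to say that following the list obliges a site to dose a contraindicated child. The gap is that the last scheduled source of information on the rule comes after the act that the rule controls.
- **Paper cards are the exception.** They are used only when an eDC cannot be. This narrows the exposure, but the documents do not say by how much.

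**Conclusion.** The point holds in a limited form. For Cohorts 2 and 4, the contraindication check and dose 2 are listed before the final collection and review of the completed diary, although item 2 of section 5.2.7.2 depends on AEs, LRI and SAEs after dose 1. Earlier contacts cover most of that record. The exposure that remains is an event not conveyed by telephone (mainly on a paper DC2), an ongoing reaction that worsened, or an SAE entered since the last call.

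The interval without a scheduled diary review is 13 to 21 days or 26 to 34 days. Which range applies depends on whether the D42 call includes a diary review, a point on which the procedures table and section 5.1.4.2 disagree. The number of children affected cannot be estimated and may well be small.

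This rests on two readings: that the numbered steps are in time order, and that relatedness in item 2 qualifies all three kinds of event. If relatedness qualifies only SAEs, the rule is wider and the case for reviewing the diary first is stronger. For Cohorts 1 and 3 the point does not arise, because no dose follows.

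**What to change.** Two places need reconciling.

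1. Visit 03 for Cohorts 2 and 4 in section 5.1.4.1, with section 5.2.7.2: list the existing diary collection and review step so that it informs the contraindication check, before the IRT call and dose 2. The contraindication rules stay as written.
2. The D42(+1) contact: the Table of Study Procedures, which marks a DC2/eDC review, and section 5.1.4.2, which lists none, should say the same thing. The matching table in the SAP (Table 3.2) should follow.

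The cost is an edit to one numbered list, one contact description and the site checklist. No visit, procedure, sample or staff is added, and no analysis changes. For children who have already had dose 2, a listing from the case report data could show any who had a qualifying event starting before that dose. It would not show when the site first learned of the event.

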- To characterize the RSV serum anti-F IgA antibody responses after the RSV season or at least 5 months after the last vaccine administration by baseline serostatus.

Exploratory Efficacy Objective

- To describe the frequency and severity of RSV-associated, medically attended acute respiratory illness (RSV MAARI) and RSV-associated, medically attended, acute lower respiratory illness (RSV MAALRI) in all infants and toddlers in each vaccine group during the RSV season or at least 5 months after last vaccine administration.

The endpoints for the exploratory objectives are presented in [Section 9.3](#).

3 Investigators and Study Organization

This study will be conducted in approximately 30 centers in the United States and approximately 10 centers in Canada, Latin America, and South Africa. Details of the study centers and Investigators at each center, are provided in the “List of Investigators and Centers Involved in the Trial” document.

An internal safety management team (SMT) will perform an analysis of safety data during the conduct of the study.

If the predetermined alert threshold for a safety event as outlined in [Section 5.1.6](#) and the SMT charter is reached, regardless of the study time point, the trial will be paused for enrollment in order for an ad hoc SMT to be convened to investigate and complete a study report, and the situation will be escalated to the Vaccine Adjudication Committee (VAC). The VAC decides whether to escalate the findings further up to the level of a Product Safety Board (PSB). Based on the recommendations of the PSB, an ad hoc Independent Data Monitoring Committee (IDMC) may be utilized to review upon request of the SMT unblinded study data and recommend to Sanofi Pasteur whether to continue, modify, or stop the study. The IDMC will make recommendations to the Sponsor on a medical and ethical basis.

The Sponsor’s Responsible Medical Officer (the RMO, the person authorized to sign this protocol and any amendments on behalf of the Sponsor) is [REDACTED].

4 Independent Ethics Committee / Institutional Review Board

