- 6) Complete the relevant CRFs for this visit.

Visit 05: D84+8 Post-Vaccination 1 (Day 28+8 Post-Vaccination 2) Visit Procedures for Cohorts 2 and 4

- 1) Review medical history, including past and ongoing medication and immunizations since the last visit.
- 2) Perform a focused clinical examination including temperature, pulse, and respirations, EENT, respiratory, cardiac and lymphatic system.
- 3) Obtain a blood sample for serum antibodies to RSV.
- 4) Collect and review the solicited reactions and unsolicited AEs, AESIs, MAAEs and SAEs in the completed DC3 / eDC with the participant's parent / guardian / legally authorized representative. Provide MA.
- 5) If an SAE had occurred, follow the instructions in [Section 10](#) for reporting it. Remind to notify the site in case of an SAE.
- 6) Complete the relevant CRFs for this visit.

Visit 99: Illness Visits

Illness visits can be conducted remotely, as a home visit or an onsite visit depending on the judgment of the investigator. The requirement for an Illness Visit and which type of illness visit will be evaluated first by video call. The video call will be used to initially remotely evaluate the study participant's clinical status and whether the illness can be managed remotely especially for mild (Grade 1) illness. This staged management of illness visits is required during the current COVID-19 pandemic situation to limit the number of contacts between the study participant and study site staff to only those that are absolutely required. Guidelines for remote evaluation are described in the Operating Guidelines.

The timeframe after site notification in which the Illness Visit must occur, if deemed necessary by the Investigator, depends on grading of the fever and respiratory symptoms and the phase of the study. If the Illness Visit occurs on a day concurrent with a routine Study Visit when a nasal swab specimen is to be collected, the same nasal swab specimen would be used to test for respiratory pathogens. A second nasal swab should be collected 48 hours later. If the Illness Visits occurs on a day concurrent with a routine Study Visit when a nasal swab specimen is not collected, a nasal

swab specimen is required to test for respiratory pathogens. A second nasal swab should be collected 48 hours.

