If illnesses/safety events occur, the study participant should be managed according to the site/local standard of care, including the conduct of lab investigations required for diagnosis and/or management of the study participant. Following an Illness Visit, medical personnel should continue to follow participants until resolution.

Illness visits may occur at any time during the study. The Illness visit timeframes are summarized in [Table 5-4](#).

Table 5-4: Illness visit timeframe

Phase	Symptom	Grade	Visit timeframe
Acute (post-vaccination to midnight 28 days after each vaccination)*	Fever, acute otitis media or URI	1	Within 3 days
		> 1	Within 2 days
	LRI	Any	Within 2 days
	SAEs	Any	Within 2 days
Post-acute (12:01am on 29 th day after post-vaccination to midnight 56 days after each vaccination)*	SAEs	Any	Within 2 days
RSV surveillance season (on average, 01 November to 31 March for NH and 01 May to 30 September for SH)*	Medically attended fever, acute otitis media, URI or LRI	>2	Within 3 days
	SAEs	Any	Within 2 days
Post-RSV season (on average, 01 to 31 April for NH and 01 to 31 October for SH) or at least 5 months after last vaccine administration	SAEs	Any	Within 2 days

LRI, lower respiratory tract illness; NH, Northern hemisphere; RSV, Respiratory Syncytial Virus; SAE, serious adverse event; SH, Southern hemisphere; URI, upper respiratory tract illness

*In some circumstances, acute phase or post-acute phase may overlap with the RSV surveillance season, in which case the more conservative visit timeframe should be considered.

Illness Visit procedures are as follows:

- 1) Obtain verbal medical history about the participant, including past and ongoing medication and immunizations.
- 2) Determine whether the participant can be managed remotely or if an at home visit or an onsite illness visit is required.
- 3) If an at home or onsite visit, perform a focused clinical examination including temperature, pulse, and respirations, EENT, respiratory, cardiac and lymphatic system. Instructions for

conducting a focused clinical examination remotely are described in the Operating Guidelines.

- 4) Collect and review the solicited and unsolicited AEs, AESIs, MAAEs and SAEs in the completed DC / eDC or memory aid with the participant's parent / guardian / legally authorized representative.

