- 5) If an SAE had occurred, follow the instructions in **Section 10** for reporting it. Remember to notify the site in case of an SAE, if illness starts within the 28 days of vaccination.
- 6) Obtain a nasal swab sample for RSV viral detection and [REDACTED] for respiratory pathogens.
- 7) COVID-19 testing if required according to the opinion of the investigator and CDC COVID testing algorithm.^a
- 8) Complete the relevant CRFs for this visit.
- 9) Schedule follow-up as appropriate, including a visit for the collection of a confirmation nasal swab 48 hour later.
- 10) If illnesses/safety events occur, the participant should be managed according to the site/local standard of care, including the conduct of lab investigations required for diagnosis and/or management of the study participant.

Specific guidance for illness visits, including use of personal protective equipment (PPE) for full contact and droplet precaution, are described in the Operating Guidelines.

Follow-up of participants with solicited reactions or with AEs That Led to Study/Vaccination Discontinuation:

Unless a participant or participant's parent / guardian / legally authorized representative refuses further contact, each participant who experiences an AE (whether serious or non-serious) during the study must be followed until the condition resolves, becomes stable, or becomes chronic (even after the end of the participant's participation in the study) if either of the following is true:

1. The AE is considered by the Investigator to be related to the product administered.
2. The AE caused the discontinuation of the participant from the study or from vaccination.

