During the RSV season (01 November to 31 March in the northern hemisphere and 01 May to 30 September in the southern hemisphere) or post-vaccination RSV surveillance (at least 5 months after last vaccine administration), make phone contacts every 2 weeks with the parent / guardian / legally authorized representative.

- 1) Record relevant information concerning the participant's health status including any changes in medications and immunizations on the telephone contact form.
- 2) Schedule an Illness Visit within the guidelines and stipulated time frame from the phone contact for a medically attended illness of the following types: fever, URI, LRI or otitis media. If this illness overlaps with the Acute or Post-Acute Phases, the time frames specified for the relevant Acute or Post-Acute phase should be used (see [Table 5-4](#)).

- 3) If a participant had visited any other non-study doctor / hospital for a serious adverse event (SAE) (at any time in the study), schedule a site visit once the participant is discharged to obtain a nasal swab sample for RSV viral detection and [REDACTED] for respiratory pathogens.
- 4) If an SAE had occurred, follow the instructions in [Section 10](#) for reporting it. Remind to notify the site in case of an SAE.

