9.3.4 Efficacy

9.3.4.1 Efficacy Endpoints

The exploratory endpoints for the evaluation of efficacy assessed through the RSV season or post-vaccination surveillance period are:

- RSV medically attended acute respiratory illness (RSV MAARI)
- RSV medically attended acute lower respiratory illness (RSV MAALRI)
- A diagnosis of RSV MAARI requires a respiratory sample positive for RSV by [REDACTED] AND documented physical exam findings of respiratory tract illness including any of the following:
 - Fever
 - Acute otitis media
 - Upper respiratory tract illness:
 - Runny nose/rhinorrhea
 - Pharyngitis
 - Cough without LRI
 - Lower respiratory tract illness (see MAALRI below)
- A diagnosis of RSV MAALRI (a subset of MAARI) requires a respiratory sample positive for RSV by [REDACTED] AND documented physical exam findings of lower respiratory tract illness including any of the following:
 - Stridor
 - Rales
 - Tachypnea
 - Acute wheeze
 - Pneumonia
 - Laryngotracheobronchitis

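### Protocol Table 5-4 and Section 5.1.4.2 disagree on which medically attended illnesses get a visit and a swab, so lower-grade RSV MAARI may be incompletely ascertained

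*Protocol*

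**What the plan says.** **Visit timing.** Table 5-4 (Protocol 5.1.4.1) sets illness-visit timeframes by phase, symptom and grade. Its RSV-season row for "Medically attended fever, acute otitis media, URI or LRI" carries Grade >2 and a three-day limit. The only other in-season row is for SAEs of any grade. The Post-Acute row and the last row (post-season, or at least five months after the last dose) list SAEs only. The Acute rows start at Grade 1 for fever, otitis media and URI, and cover LRI of any grade.

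**Telephone contacts.** Section 5.1.4.2, which applies in season and during post-vaccination surveillance, tells sites: "Schedule an Illness Visit within the guidelines and stipulated time frame from the phone contact for a medically attended illness of the following types". It then lists fever, URI, LRI and otitis media and states no grade.

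**Role of grade.** Section 5.1.4.1 says: "The timeframe after site notification in which the Illness Visit must occur, if deemed necessary by the Investigator, depends on grading". It also says: "Illness visits may occur at any time during the study".

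**Overlapping phases.** The footnote to Table 5-4 covers acute or post-acute phases that run into the season, "in which case the more conservative visit timeframe should be considered". Section 5.1.4.2 instead says to use the timeframe of the relevant Acute or Post-Acute phase.

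**Endpoint.** Protocol 9.3.4.1 states: "A diagnosis of RSV MAARI requires a respiratory sample positive for RSV by" a named assay (redacted), together with any one of the listed findings at any severity. The illness-visit procedures include: "Obtain a nasal swab sample for RSV viral detection and" a pathogen test. SAP 4.4.3 takes the efficacy events from illness visits.

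**The concern.** A case that is not swabbed cannot become an RSV MAARI, whatever its clinical picture. If the graded row decides who is swabbed, the endpoint is ungraded on paper and graded in practice.

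The row may leave out the ordinary attended case. On the nasal-symptom scale in Protocol Table 9-1, outpatient care by a provider is already Grade 2. On the DAIDS scale in Table 9-3, Grade 3 is severe illness that prevents usual activities.

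Three things are at stake: the case count, the severity description (Protocol 2.3 asks for frequency and severity together), and the vaccine efficacy that SAP 5.1.3 computes from confirmed cases. Sites that act on different passages would also ascertain cases differently.

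**Working it through.** **1. The passages side by side.** This is what each says about a medically attended, non-serious illness of Grade 1–2:

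| When it occurs | Table 5-4 | Section 5.1.4.2 |
|---|---|---|
| In season, outside acute and post-acute phases | No timeframe listed | Visit, no grade stated |
| In season, overlapping the acute phase | Acute row, by the footnote | Acute timeframe |
| In season, overlapping the post-acute phase | Footnote: the more conservative of an SAE-only row and a Grade >2 row | Post-acute timeframe, which is SAE-only |
| Post-vaccination surveillance, outside season and acute phase | SAEs only | Visit, no grade stated |

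The passages agree in the second line only. In the last line the gap applies at every grade.

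**2. The last line can be long.** Take a northern-hemisphere Cohort 4 participant enrolled on 1 January. Dose 2 at D56 falls on 26 February, the second acute phase ends 28 days later on 26 March, and the season ends on 31 March. Five months after dose 2 is 26 July. From 1 April to 26 July (30 + 31 + 30 + 26 = 117 days), Table 5-4 has no row for non-serious attended illness, yet Protocol 5.1.2 says such participants are monitored for it.

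**3. The plan's own figures.** The only sample-size-linked figures (Protocol 12.5, SAP 5.5) concern the chance of seeing at least one event. They reproduce: 1 − 0.97^100 = 95.2% and 1 − 0.9625^80 = 95.3%, against 95% stated for each. They do not bear on swabbing. The documents give no RSV attack rate and no grade distribution.

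**4. Illustration on assumed inputs.** Let a be the medically attended RSV attack rate on placebo and s the share swabbed. Expected confirmed cases = N × a × s, and P(none) = (1 − a·s)^N. Placebo N is 120 pooled and 60 in Cohort 4. With a = 10%:

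| s | Expected, N = 120 | P(none) | Expected, N = 60 | P(none) |
|---|---|---|---|---|
| 100% | 12 | <0.1% | 6 | 0.2% |
| 50% | 6 | 0.2% | 3 | 4.6% |
| 25% | 3 | 4.8% | 1.5 | 22% |
| 10% | 1.2 | 30% | 0.6 | 55% |

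For a from 5% to 20%, expected pooled placebo cases run from 6–24 (all swabbed) down to 0.6–2.4 (10% swabbed). At a = 15% and s = 10%, Cohort 4 gives 60 × 0.15 × 0.10 = 0.9 cases and P(none) = 0.985^60 = 40%. Pooled, it gives 1.8 cases and 0.985^120 = 16%.

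**5. Effect on the VE interval.** SAP 5.1.3 uses VE = 1 − (N_P/N_RSV) × q/(1 − q), with a Clopper-Pearson interval for q, the RSV arm's share of cases. Assume a true VE of 50%, with 100 low-dose and 120 placebo participants:
- 12 placebo and 5 low-dose cases (all swabbed): VE 50%, 95% CI about −52% to 86%.
- 3 placebo and 1 low-dose case (about a quarter swabbed): VE 60%, 95% CI about −398% to 99%.

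**6. Bias as well as precision.** If the arms have different swabbed shares, the VE estimated is 1 − (s_RSV/s_P) × (1 − VE). Equal shares leave it unchanged. If vaccination makes illness milder and only severe illness is swabbed, s_RSV falls below s_P. At an assumed ratio of one half, a true 50% would read as 1 − 0.5 × 0.5 = 75%. That is efficacy against severe illness under the MAARI label.

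**The case against.** The strongest reply is that Table 5-4 sets timing and does not decide who is seen. Its title says timeframe, the text ties grade to how soon a visit must occur, and visits are allowed at any time. The working instruction for surveillance is Section 5.1.4.2, which has no grade. SAE visits and acute-phase overlap also bring in lower-grade swabs. All of this stands. A reader might infer that Grade 1–2 illness gets no swab, that most RSV cases cannot be laboratory-confirmed, and that MAARI is therefore Grade 3 or worse under another name. The documents do not support that: nothing bars a lower-grade visit, and no figure shows what share would be lost.

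The timing reading does not remove the conflict, however. Section 5.1.4.2 asks for the visit within a stipulated timeframe, and none is stipulated for Grade 1–2 illness in season. Section 5.1.4.1 leaves the need for a visit to the investigator, limits contacts to those strictly needed during the pandemic, and lets mild illness be managed remotely. A site can follow all of that and take no swab.

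The sign is also uncertain. The Acute rows pair Grade 1 with >1, which works as a strict inequality. But the schedule of procedures prints >5 months where its footnote says at least five. If ≥2 was meant, only Grade 1 is at issue in season.

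The last row of Table 5-4 may describe only the closing visit window. In that case the table has no row at all for off-season surveillance, so the gap remains.

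Finally, safety assessors are blinded (Protocol 6.4), so no difference by arm is expected at a given grade. The VE interval is also wide under full swabbing. Both points stand, and they limit the consequence.

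**Conclusion.** The protocol contradicts itself on whether a medically attended Grade 1–2 illness in the RSV season prompts a visit, and so a swab. It is also unclear for any non-serious attended illness during post-vaccination surveillance outside the season and acute phase, and the two overlap rules differ. Because RSV MAARI is ungraded and needs a positive sample, lower-grade cases may be missed, to an extent that may vary by site. The frequency, severity and VE results would then lean towards severe illness.

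The size of the loss cannot be derived from the documents. The case counts and intervals above rest on assumed attack rates, swabbed shares and a 50% VE, and show direction only. The post-season titer can reveal a missed infection but cannot confirm a MAARI. The effect is confined to an exploratory, descriptive endpoint and touches no primary or secondary objective.

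**What to change.** **Protocol.** Reconcile Table 5-4 with Section 5.1.4.2 on grade, on surveillance outside the calendar season and on overlapping phases, and confirm the intended sign in the season row. The swabbing rule used for endpoint ascertainment should match the ungraded MAARI definition. How ill children are managed is a separate matter for the sponsor and investigators, and this point proposes no rule for it.

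**SAP.** Add one table of medically attended febrile or respiratory illnesses during surveillance, swabbed and not swabbed, by grade and arm. State any limit on ascertainment according to what sites actually did. The SAP should not declare in advance that only Grade 3 or above was captured, since that may be untrue.

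**Cost.** Table wording and one extra output, with no more swabs than Section 5.1.4.2 already asks for. For visits already past, only the SAP change applies. It lets a reader tell whether few confirmed cases mean few illnesses or few swabs.
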